To answer questions 1a and 1b, we will fit mixed model repeated measures (MMRM) models which account for missing data as an integral part of the analyses under the assumption of ignorable missing. To answer question 1a, the MMRM model includes longitudinal pain score (0-10 NRS on Tampon Test) as a continuous outcome variable; includes fixed effect terms for treatment (nortriptyline, lidocaine/estradiol, and their interaction), visit, treatment visit interaction, center, and fixed effect covariates vector including age, VBD subtype (binary variable where VBD-c is coded as 0 and VBD-p coded as 1), race (three levels "white", "black" and "other" race, coded into two binary dummy variables with European American serving as a reference level).

Overall treatment effect of nortriptyline, lidocaine/estradiol, and their interaction will be evaluated using an F-test. If significant ($p < 0.05$), treatment differences (each of 3 treatment groups minus placebo) in the Least-Squares means (LS means), their 2-sided 95% CIs, and associated p-

values will be estimated from the MMRM model. P-values will be compared with the significance threshold Bonferroni-corrected for 3 tests (i.e. alpha 0.0166).

To answer question 1b, we will fit a MMRM model analogous to 1a, with additional terms of VBD subtype visit interaction, treatment VBD subtype interaction, and treatment visit VBD subtype interaction. The significance of the additional interaction terms will be evaluated using a F-test comparing the full model in 1b and the reduced model in 1a. Significant ($p < 0.05$) F-test will suggest that the effect of either nortriptyline or lidocaine/estradiol cream, or both, differ by VBD subtype. In this case, we will compare the LS means of the treatment differences in each treatment-VBD-subtype subgroup, after appropriate Bonferroni correction.

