To answer question 2a, we will fit three linear regression models with the dependent continuous variable being a variable for each of the 3 patient reported outcomes (SF12 physical health score, SF12 mental health score, and PROMIS sexual health score). VBD subtype will be the predictor of interest. Covariates will include age (continuous variable), race (coded as in model 1a), study site. Regression coefficient for VBD subtype will be tested for statistical significance using Bonferroni-corrected threshold alpha 0.0166 (corrected for 3 tests corresponding to 3 outcomes). Regression coefficient significance will suggest outcomes differ by VBD subtype.

To answer question 2b, three MMRM models analogous to model 2b will be fit, where Y is a continuous variable representing the primary outcomes measured at 16 weeks. Similar to 2b, we will jointly evaluate the significance of additional interaction terms using an F-test (“overall test”). Significant F-test will suggest that the effect of either nortriptyline or lidocaine/estradiol cream, or both, differ by VBD subtype. In this case, we will compare the LS means of the treatment differences in each treatment-VBD-subtype subgroup, after appropriate Bonferroni correction. Secondary outcomes will also include change in SCL-27 mood score, PILL somatization score, and PROMIS biopsychosocial trait scores from baseline to 16 weeks following treatment. Secondary outcomes also include change in patient-reported outcomes from baseline to the 8-week time point and change in pain scores and PPTs from the 16-week to the 24-week time point.

Expected Outcomes. **1)** For women with VBD-p, peripheral lidocaine/estradiol treatment will be more effective than placebo or nortriptyline in improving perceived physical, mental, and sexual health at 8 and 16 weeks. **2)** For women with VBD-c, centrally-targeted nortriptyline treatment will be more effective than placebo or lidocaine/estradiol in improving perceived physical, mental, and sexual health at 16 weeks. **3)** For women with VBD-c, combined peripheral and centrally-targeted treatments will be most effective in improving health at 16 weeks. **4)** The two VBD subtypes will exhibit differential responses to treatment withdrawal, such that women with VBD-c report decreases in perceived health from 16 to 24 weeks compared to women with VBD-p.

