15.4 Analysis of the Aim 3 Endpoints

Cytokine Expression levels will be measured in vaginal lavage samples and plasma isolated from whole blood. We will use a standard Human MesoScale Discovery multiplex kit to measure 36 inflammatory mediators (4 tier-1 and 32 tier-2).

Tier-1 mediators include the pro-inflammatory cytokines IL-1 β ,⁵⁹⁻⁶¹ IL-8,^{7,60,62} and IL-17⁶³ and anti-inflammatory cytokine IL-1ra.^{7,61} These cytokines were selected based on previous associations with VBD case status and symptom severity.

Tier-2 mediators include cytokines (e.g., interleukin 6; IL-6), chemokines (e.g., monocyte chemoattractant protein 1; MCP1), and growth factors (e.g., vascular endothelial growth factor; VEGF) that are involved in peripheral and central sensitization, inflammation, and chronic pain.¹²⁸

miRNA Expression levels will be measured in vaginal swab samples and blood. We will isolate total RNA and then ship the RNA to UT Health Genome Sequencing Facility (GSF), directed by [name]. The GSF core will perform small RNA library preparation and sequencing.

Data Analysis. The two primary statistical questions for Aim 3 are: 3a) At baseline, is there an inverse association between VBD 'centralness' score (determined by the number of COPC sites) and the levels of Tier-1 cytokines in vaginal samples; and a positive association between VBD 'centralness' score and the levels of Tier-1 cytokines in plasma samples? 3b) Do biomarkers in vaginal fluid predict response to peripheral treatment and biomarkers in blood predict response to central treatment?

To answer question 3a, we will fit a linear regression model where cytokine level (skewed variables will be transformed (e.g., log, box-cox) to approximate normal distribution) will be a continuous dependent variable and VBD 'centralness' score, will be the main predictor of interest. Covariates will include age and race. Significance of regression coefficient associated with the 'centralness' score will be evaluated using an F-test and significance threshold (alpha) Bonferroni-corrected for the number of cytokines assessed (4 cytokines corresponding to 4 statistical tests). Subgroup means, mean differences and 95% confidence intervals will be output.

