15.6 Sample Size and Power

We are planning to enroll 400 women with VBD, with an estimated attrition rate of 20%. Of note, Reed et al. found that vulvar pain measured on a 0-10 numeric scale has standard deviation 2.0.¹⁰⁴ Salaffi et al¹⁰⁵ noted that 2 points on a 0-10 NRS correspond to a clinically meaningful difference in pain severity. Using these results and assuming the within-subject correlation of 0.5, at a significance level of 0.05, the proposed sample size will provide sufficient power of at least 0.80 to detect differences as small as 0.82 on a 0-10 scale for the overall treatment main effects (3 arms) vs. placebo. To test each individual treatment effect vs. placebo, at a significance level of 0.0167 (Bonferroni-corrected for 3 arms), the proposed sample size can detect differences as small as 0.98 on a 0-10 scale. At a significance level of 0.05, the proposed sample size can detect differences as small as 1.35 and 1.20 on a 0-10 scale for the interaction effect of treatment and each VBD-subtype, given possible splits of 40/60, 50/50, or 60/40 (of note, VBD-p vs VBD-c frequencies were 40/60 at UNC and 50/50 at UCLA clinics in previous studies).

To calculate power for research question IIIa, we used data from our previous study of biomarkers in VBD patients.⁷ Conservatively assuming that VBD-c patients represent 60% (192/320) of the sample and VBD-p patients represent 40% (128/320) of the sample, and adjusting the significance threshold for 4 tier 1 cytokine tests, we will be able to detect mean differences of at least 0.4 SD with the power of 0.84 or greater using a t-test. For IL-8, 0.4 SD translates to approximately 2 pg/mL, and for IL-1ra 0.4 SD translates to 240 pg/mL of the minimal detectable difference. Of note, the mean differences between controls and VBD patients for IL-8 and IL-1ra in our previous study were 4 pg/mL and 300 pg/mL, respectively. Thus, we have sufficient power to detect plausible differences in cytokine levels between the VBD subgroups.

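### Section 15.2 tests the three active-versus-placebo contrasts at a fixed Bonferroni threshold; Holm's step-down would keep the same 0.05 family-wise bound and, when two or three arms work with effects near 1 point, give more power

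*Combined protocol and SAP*

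**What the plan says.** Section 15.2 sets a two-stage test for question 1a. First comes the gate: "Overall treatment effect of nortriptyline, lidocaine/estradiol, and their interaction will be evaluated using an F-test". If it is significant at 0.05, the model yields "treatment differences (each of 3 treatment groups minus placebo) in the Least-Squares means (LS means), their 2-sided 95% CIs" and p-values. For these, "P-values will be compared with the significance threshold Bonferroni-corrected for 3 tests (i.e. alpha 0.0166"). The same threshold applies to all three contrasts, whatever the other two show.

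Section 15.6 sizes the contrasts on the same rule: "at a significance level of 0.0167 (Bonferroni-corrected for 3 arms), the proposed sample size can detect differences as small as 0.98", on the 0-10 scale. It gives the value as 0.0167, where 15.2 has 0.0166.

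Fixed Bonferroni thresholds also appear in two baseline analyses. In Section 15.3 (question 2a) the subtype coefficients are "tested for statistical significance using Bonferroni-corrected threshold alpha 0.0166 (corrected for 3 tests corresponding to 3 outcomes"). In Section 15.4 (question 3a) there is a "significance threshold (alpha) Bonferroni-corrected for the number of cytokines assessed", which is four. Sections 15.2 and 15.3 also promise a Bonferroni correction for the 1b and 2b follow-up comparisons, without listing or counting them. No step-down procedure is mentioned anywhere.

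**The concern.** Question 1a asks whether cream, nortriptyline or the combination beats placebo, so several true effects are a case the trial has to handle well. With a single-step threshold, the third contrast must still reach 0.0166 when the first two have been shown convincingly. Holm orders the p-values, compares the smallest with 0.05/3, the next with 0.05/2 and the last with 0.05, and stops at the first failure. Its bound holds under any dependence, so the shared placebo arm is no obstacle. It rejects everything that Bonferroni rejects.

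The usual reason to keep the single-step rule is that it has matching simultaneous intervals. The plan does not use that advantage, because its intervals are ordinary 95% ones. As written, a contrast with p between 0.0166 and 0.05 is called non-significant beside an interval that excludes zero. At stake is a higher chance of missing a second or third effective treatment.

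**Working it through.** **Inputs.** From Section 15.6: SD 2.0, within-subject correlation 0.5, power at least 0.80, 400 women, 20% attrition, 2 points as the clinically meaningful difference. From Section 5.3: 1:1:1:1 allocation, so 100 per arm. The correlation leaves the SD of a change at 2.0 × √(2 × (1 − 0.5)) = 2.0.

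**Assumption.** The plan does not say when the attrition occurs. If it accrues evenly to week 24, two thirds has happened by week 16: 100 × (1 − 0.20 × 16/24) = 86.7 per arm. If all of it precedes week 16, 80 per arm remain.

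**The plan's own figure.** Detectable difference = (z for 1 − α/2 + z for power) × SD × √(2/n). With α = 0.05/3 = 0.01667 the z-values are 2.394 and 0.842.

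- n = 86.7: 3.236 × 2 × √(2/86.7) = 0.983, which matches the stated 0.98. Power at 0.98 is 0.797.
- n = 80: 3.236 × 2 × √(2/80) = 1.023. Power at 0.98 is 0.760.
- n = 100: 0.915. Power at 0.98 is 0.858.

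At n = 86.7 a 3-df F-test at 0.05 has a detectable difference of 0.824. This agrees with the other stated figure, "differences as small as 0.82 on a 0-10 scale for the overall treatment main effects (3 arms) vs. placebo".

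**Comparison.** I simulated 400,000 trials per scenario: four arms, shared placebo, pooled variance, F-test gate at 0.05, then either fixed 0.0166 or Holm. Power counts only arms with a true effect. Repeat runs differ by about 0.002.

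| True effects (points) | n per arm | Per contrast: Bonferroni / Holm | All true effects shown | At least one |
|---|---|---|---|---|
| 0.98, 0.98, 0.98 | 86.7 | 0.786 / 0.851 | 0.601 / 0.760 | 0.924 / 0.924 |
| 0.98, 0.98, 0.98 | 80 | 0.744 / 0.814 | 0.545 / 0.712 | 0.899 / 0.899 |
| 0.98, 0.98, 0 | 86.7 | 0.792 / 0.821 | 0.678 / 0.734 | 0.906 / 0.907 |
| 0.98, 0, 0 | 86.7 | 0.786 / 0.788 | as per contrast | as per contrast |
| 2, 2, 2 | 86.7 | 1.00 / 1.00 | 1.00 / 1.00 | 1.00 / 1.00 |
| 0.98, 0.98, 1.96 | 86.7 | single agents 0.793 / 0.876 | 0.678 / 0.819 | 1.00 / 1.00 |

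The small differences in the one-effect row come from 0.0166 against 0.0167 and from rare step-down cases.

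**Family-wise error, gate kept, n = 86.7, Bonferroni / Holm.** No true effect: 0.029 / 0.029. One true effect of 2 points: 0.031 / 0.046. Two true effects of 2 points: 0.016 / 0.050. Both rules respect 0.05, and Holm uses the part that Bonferroni leaves unspent.

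**The case against.** The strongest reply is that nothing is wrong. The threshold is valid, prespecified and the one the trial was sized on, so no promised power is lost. That stands. A reader might infer that the trial gives up power for nothing, or is underpowered because of Bonferroni. The documents support neither: the sizing already carries the correction, and the chance of at least one success is the same under both rules.

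Second, the gain is confined to particular scenarios. With one effective arm, or with 2 points in every arm, it is nil. That also stands, but 2 points in every arm is not what the protocol hypothesises. It expects the peripheral subtype to prefer the cream and the central subtype to prefer central or combined treatment, while the 1a model has no treatment-by-subtype term. For illustration, suppose a single agent gives 2 points in one subtype and none in the other. At the 40/60 to 60/40 splits in Section 15.6, its pooled effect is 2 × 0.4 = 0.8 to 2 × 0.6 = 1.2, the range where Holm helps.

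Third, equal error control means an equal bound, not equal actual error: a null arm is falsely declared effective more often when the other arms work. And a single-step rule could be paired with 98.33% intervals (1 − 0.05/3), whereas Holm has no equally simple match. Both points stand. The second would weigh more if the plan reported such intervals.

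Fourth, the simulation says nothing about 2a and 3a, which are baseline regressions without arms. Holm is valid there, but no gain has been computed. For the 1b and 2b follow-ups it cannot be applied until the comparisons are listed.

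**Conclusion.** This is a cheap efficiency improvement to a valid rule, not the correction of an error. In the most favourable equal-effect case (all three at 0.98), Holm adds about 6.5 to 7 percentage points per contrast and about 16 to 17 points to the chance of showing all three. With two effective arms it adds about 3 points per contrast. The figures rest on SD 2, 80 to 87 evaluable women per arm (assumed, since the timing of attrition is not stated) and the F-test gate kept. A simple two-sample comparison stands in for the repeated-measures model. The 0.05 family-wise bound does not depend on these assumptions.

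**What to change.** - **Section 15.2:** after the F-test, compare the ordered p-values of the three contrasts with 0.0167, 0.025 and 0.05, stopping at the first that fails. State that the 95% intervals are not adjusted for multiplicity and that decisions rest on the Holm-tested p-values.
- **Section 15.6:** keep 0.98 as the first-step figure and align 0.0166 with 0.0167. State when the 20% attrition is assumed to occur, because 0.98 depends on it.
- **Sections 15.3 and 15.4:** the same substitution may be made for the three outcomes in 2a and the four Tier-1 cytokine tests in 3a, without claiming a quantified gain.
- **1b and 2b follow-ups:** leave unchanged until their comparisons are listed and counted.

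The cost is a few sentences and a line of programming, fixed before unblinding. It needs no further participants or data. What is given up is the unused margin below 0.05 and the option of simple simultaneous intervals.

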To answer question 3b, we will fit a MMRM model analogous to 1a, with additional terms of treatment cytokine (in blood and vaginal samples) interaction, visit cytokine interaction, and treatment visit cytokine interaction. Significance of additional interaction terms will be evaluated using an F-test. Significant ($p < 0.05$) F-test will suggest that treatment effects by nortriptyline or lidocaine/estradiol cream or both, are modified by cytokines.

Secondary analyses for Aim 3 will include the association of Tier 2 biomarkers (cytokines and miRNAs) with VBD subtype and interaction with treatment response. These analyses will be analogous to those specified for questions 3a and 3b, with p-value thresholds kept at 0.05 due to exploratory nature of these analyses. In our secondary analyses we will also evaluate the change of biomarker concentrations (blood and vaginal samples) over time (at 0, 8, 16, and 24 weeks) in each treatment group and VBD subtype. We hypothesize that these biomarkers may serve as intermediate phenotypes for treatment success in VBD patient subgroups.

Expected Outcomes. 1) Women with VBD-p will have higher levels of inflammatory mediators in peripheral vaginal samples, while women with VBD-c will have higher levels of inflammatory mediators in circulating blood measured at the baseline visit (0 weeks). 2) Abnormalities in baseline vaginal cytokine and miRNA biomarkers will predict a positive response to peripheral lidocaine/estradiol treatment, while abnormalities in blood biomarkers will predict a positive response to centrally-targeted nortriptyline or combined treatment. 3) Peripheral treatment will resolve abnormalities in vaginal biomarkers evaluated at 8, 16, and 24 weeks, while central treatment will resolve abnormalities in blood biomarkers evaluated at 16 weeks.

All analyses will be performed using the Intent-to-Treat (ITT) population. The ITT population will include all randomized participants. Participants will be grouped according to their randomized allocation, regardless of whether the allocated therapy was administered or switched.

Any deviations from the statistical analyses described above, due to unforeseen circumstances, will be documented in the Statistical Analysis Plan (SAP).

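### The 1b F-test (and 3b; 2b if it has visit terms) includes a term without treatment, so a prognostic gap that changes over visits can be read as a treatment effect that differs by subtype

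*Combined protocol and SAP*

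**What the plan says.** Section 15.2 defines model 1a with treatment, visit, treatment-by-visit, center and a "fixed effect covariates vector including age, VBD subtype (binary variable where VBD-c is coded as 0 and VBD-p coded as 1"), plus race. Subtype therefore enters 1a as a main effect only. Model 1b is the same model "with additional terms of VBD subtype visit interaction, treatment VBD subtype interaction, and treatment visit VBD subtype interaction". The test is stated in one sentence: the "additional interaction terms will be evaluated using a F-test comparing the full model in 1b and the reduced model in 1a". A result with p<0.05 "will suggest that the effect of either nortriptyline or lidocaine/estradiol cream, or both, differ by VBD subtype", and within-subtype treatment contrasts with Bonferroni correction follow. A significant 1a or 1b also opens the analysis of further primary outcomes. A non-significant 1b leads instead to the analysis with the continuous COPC score.

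Section 15.4 builds model 3b from 1a with "additional terms of treatment cytokine (in blood and vaginal samples) interaction, visit cytokine interaction, and treatment visit cytokine interaction". A significant F-test "will suggest that treatment effects by nortriptyline or lidocaine/estradiol cream or both, are modified by cytokines". No cytokine main effect is listed there or in 1a, and the reduced model is not named.

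Section 15.3 says for question 2b that "we will jointly evaluate the significance of additional interaction terms using an F-test". It describes the model as analogous to model 2b, that is, to itself, and describes the outcome as measured at 16 weeks.

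**The concern.** An F-test of a full against a reduced model tests every term by which the two differ. Between 1a and 1b, one of those terms is subtype-by-visit. It is non-zero whenever the two subtypes follow different pain courses, even if the difference is identical in all four arms, placebo included. The joint null hypothesis can then be false although no treatment effect differs by subtype, so the stated conclusion does not follow from the stated test.

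Test 3b has the same structure with visit-by-cytokine. If the cytokine main effect is really absent, the tested terms also pick up a plain, constant association between cytokine and pain.

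These tests carry the trial's central hypotheses on subtype-specific and biomarker-specific response. A false-positive 1b would support the main claim, open further primary outcomes and bypass the COPC-score analysis.

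**Working it through.** **Inputs from the documents.** 400 randomized with 20% attrition, so 400 × 0.8 = 320; SD 2.0; within-subject correlation 0.5; splits 40/60, 50/50 or 60/40 (Section 15.6). Allocation 1:1:1:1 (Section 5.3). Visits at weeks 0, 8, 16 and 24 (Section 4).

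**Assumptions, not in the documents.** Equal correlation between all visits; 320 women with complete data; the subtype gaps d and the cytokine–pain correlations used below. Throughout, no treatment effect is modified by subtype or cytokine.

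**The plan's own figures.** The plan gives no error rate or power for the joint F-test. The nearest figures are the detectable differences of 1.35 and 1.20 for treatment and subtype. With 80 per arm, one arm against placebo inside a subtype gives (1.960 + 0.842) × 2 × √(2/n): 1.40 for n = 32 (40%) and 1.25 for n = 40 (50%). A repeated-measures calculation with 100 per arm, correlation 0.5 and an assumed retention of 100/90/80/80% gives 1.36 and 1.215. SD 2.0 and correlation 0.5 therefore reproduce the plan's figures closely and are used here. They say nothing about the joint test.

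**Degrees of freedom for 1b.** With three post-baseline visits: subtype-by-visit 2, treatment-by-subtype 3, three-way 6, total 11. With week 0 as a fourth outcome visit: 3 + 3 + 9 = 15.

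**Noncentrality for 1b.** Let g be the subtype gap at each visit, equal in all arms. The main effect in 1a absorbs its mean, so

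λ = Σ(g − mean g)² × N·p(1 − p) / [SD²(1 − r)].

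With N = 320 and p = 0.4, the multiplier is 320 × 0.24 / (4 × 0.5) = 76.8/2 = 38.4.

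- Constant gap of any size: the sum is 0, λ = 0, rejection 5%.
- Gap wider by d at week 24 only, three visits, sum = (2/3)d² (noncentral chi-square, 11 df):

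| d | sum | λ | rejection |
|---|---|---|---|
| 0.5 | 0.167 | 6.4 | 33% |
| 0.75 | 0.375 | 14.4 | 72% |
| 1.0 | 0.667 | 25.6 | 95% |

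- The same with week 0 included and the gap unchanged there: sum = 0.75d², λ = 7.2, 16.2, 28.8, 15 df, rejection 32%, 72%, 96%.
- A noncentral F in place of chi-square gives 32%, 70%, 95% for the three-visit case.
- Linear drift from 0 at week 0 to d at week 24, four visits, 50/50 split: sum = 0.556d², multiplier 320 × 0.25/2 = 40, λ = 5.6, 12.5, 22.2; noncentral F gives 24%, 55%, 86%.
- Simulation (2,000 runs, four visits, 50/50 split): a gap that changes by 0.5 or 1.0 after baseline gives 31% or 96%; a constant gap of 2 points gives 4.3%.

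**Test 3b, read literally.** Without a main effect, the tested terms span a separate cytokine slope for each arm and visit: 4 × 3 = 12 df. A correlation c with pain, equal in all arms and visits, gives a slope of 2c points per SD of cytokine. The mean of three visits has variance 4 × (1 + 2 × 0.5)/3 = 2.667, so λ = 320 × (2c)²/2.667.

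- c = 0.1: λ = 4.8, rejection 24%.
- c = 0.2: λ = 19.2, rejection 85%.
- Four visits (variance 2.5, 16 df): λ = 5.12 and 20.48, rejection 22% and 83%.
- Cytokine main effect in the reduced model: 5% for the same constant association.

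**After the correction.** With subtype-by-visit in both models, 1b has 3 + 6 = 9 df (three visits) or 3 + 9 = 12 df (four). Rejection is 5.0% in every prognostic scenario above; the simulation gives 5.4%.

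**The case against.** The best defense is that the harm is narrower than it looks.

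- **Subtype main effect.** A reader might infer that any prognostic subtype would be declared a modifier. The documents do not support that: subtype is already in 1a, and a constant gap is rejected 5% of the time. The error needs a gap that changes over visits. This stands.
- **Test 3b.** Section 15.4 lists additional terms in prose and does not say that the cytokine main effect is left out. If it is meant to be in the reduced model, the 24% and 85% fall away and only the visit-by-cytokine fault remains. This stands as a limit on the figures.
- **Test 2b.** A reader might infer that 2b copies the fault. If the outcome is the week-16 value alone, there are no visit terms and the fault is absent. The text does not settle this.
- **Size.** The gaps and correlations are assumed. The first 1b scenario puts the whole change at week 24, after treatment has stopped. The plan's fourth expected outcome in Section 15.2 concerns response to withdrawal, which does not imply an equal divergence under placebo. Linear drift gives lower rates.
- **Follow-up contrasts.** A reader might infer that the within-subtype comparisons after 1b are invalid. They come from a model that contains subtype-by-visit and are not biased by a prognostic course.

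None of this rescues the stated reading of a significant 1b or 3b. That reading attributes to treatment a result that a term without treatment can produce.

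**Conclusion.** The concern holds in limited form. Tests 1b and 3b, as written, cannot support the conclusion attached to them, because each jointly tests a term that does not contain treatment. For 1b the false-positive rate stays at 5% when the prognostic gap is constant. It reaches about 33%, 72% or 95% for an assumed widening of 0.5, 0.75 or 1.0 points at week 24 only, and about 24%, 55% or 86% for linear drift. For 3b, a constant correlation of 0.1 or 0.2 (assumed) gives about 24% or 85% if the cytokine main effect is absent, and 5% if it is in the reduced model. For 2b the fault is conditional on visit terms being intended.

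The structural fault in 1b and 3b follows from the text. The rates depend on assumed gaps and correlations and show what could happen, not what is expected. The uncontrolled statement is the general one that treatment effects differ, together with the steps that a significant 1b opens or bypasses. The within-subtype contrasts themselves are not biased.

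**What to change.** - **1b:** put subtype-by-visit in the reduced model alongside the subtype main effect. Test only treatment-by-subtype and treatment-by-visit-by-subtype (9 df with three visits, 12 df with four), and state which visits are outcomes.
- **3b:** name the reduced model and put the cytokine main effect and cytokine-by-visit in it. Test only terms that contain treatment.
- **2b:** correct the self-reference and say whether the model has visit terms. If it does, apply the 1b correction.

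The cost is SAP wording and a different contrast statement, with no effect on data collection; the change should be made before unblinding. There is some loss of nominal power. If one arm's effect truly differs by subtype by 1.2 or 1.35 points after baseline (four visits, 320 completers, 50/50 split), rejection falls from about 68% to 63%, or from about 81% to 75%. Part of the difference is rejection obtained through the term without treatment.

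A 3-df contrast at week 16, and reporting within-subtype differences with confidence intervals whatever the F-test shows, are reasonable options but are not needed to correct this error.
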